#### 13.1.3 Study early stopping rules

Study enrollment will be suspended pending expedited review of all pertinent data by the IRB and the DSMB if any one of the following occurs:

- Death from any cause in any subject believed to be related to study drug
- Multiple medically similar serious adverse events related to study medication
- Events that, in the opinion of the Principal Investigator contraindicate further dosing of additional subjects

If one of the above-listed stopping rules are met, a prompt cumulative review of safety data and of the circumstances of the event(s) in question will be conducted to determine whether study entry should be resumed, whether the protocol will be modified, or whether the study will be discontinued permanently. Review and approval by the DSMB is required for resumption of the study in the event the study is interrupted because of one of the above-listed events.

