### **5.6 Treatment Regimen:**

We have chosen an intra-patient dose escalation strategy because there is no previous data from human studies to demonstrate the safety of resveratrol in combination with sirolimus, in patients with LAM. Patients will begin resveratrol at a starting dose of 250mg daily, and increase the dose to 500mg daily after 8 weeks, followed by dose escalation to 1000mg daily in two divided doses (500 mg twice a day) at week 16 of the study. If no adverse effects are seen, patients should reach a dose of 1000mg per day at week 16 of the study, and then continue with this dose for the rest of the study duration. If patients do not tolerate a certain dose of resveratrol, the dose will be reduced to the last tolerated strength. Patients will remain on the last well-tolerated dose of resveratrol for the entire study duration. Patients will remain on their current dose of sirolimus without interruption, as clinically indicated. Patients who are unable to tolerate the lowest dose of resveratrol will be withdrawn from the study.

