## 7. Stopping rules

### 7.1 Participant withdrawal criteria

Participants may be terminated early from the study for the following reasons:

- a. The participant elects to withdraw consent from all future study activities, including follow-up.
- b. The participant is “lost to follow-up” (i.e., no further follow-up is possible because attempts to reestablish contact with the participant have failed).
- c. The participant dies.
- d. The participant develops a medical condition or is started on new medication(s) not previously mentioned in the list of prohibited medications that, in the opinion of the investigator, may pose additional risks from participation in the study, may interfere with the participant’s ability to comply with study requirements or that may impact the quality of the data obtained from the study.
- e. The participant is listed for transplant and is required to stop sirolimus therapy.
- f. In the opinion of the investigator, it is not in the participant’s best medical interest to continue to participate in the study.
- g. The participant meets any of the individual stopping rules as delineated in section 13.1.

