### 7.2 Criteria for terminating the study

Up to 25 patients will be enrolled in this study. The maximum duration of patient participation is up to 28 weeks, including a follow-up phone contact 4 weeks after the last study visit. In the event of any death, or Grade IV Serious adverse event (SAE) attributable to the study agent and unexpected, enrollment will be suspended, pending Data Safety Monitoring Board (DSMB) review.

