## 13. Procedures

### 13.1 Stopping rules

#### 13.1.1 Study discontinuation

The DSMB, FDA, and IRB have the authority to stop or suspend this trial at any time. This study may be suspended or closed if:

- Early stopping rules have been met
- The study objectives have been met
- The study chair/investigators believe it is not safe for the study to continue
- The DSMB suspends or closes the trial
- The FDA suspends or closes the trial

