#### **13.1.4 Individual early stopping rules**

A study participant will be terminated from the study if any of the following occurs during the study:

- Recurrent or persistent resveratrol-related toxicity unresponsive to treatment in spite of dose adjustments.
- Pregnancy or failure to comply with adequate contraception
- The participant refuses to continue in the study
- Continued non-compliance
- The investigator determines that the participant should be withdrawn from the study for reasons not listed above

A subject will be considered evaluable if they receive treatment for at least 8 weeks and the relevant information collected during this period. Subjects who are withdrawn after less than 8 weeks of treatment will be considered as pre-mature discontinuation, and will be replaced by another participant.

Every effort will be made to obtain endpoint evaluations for subjects who withdraw or who discontinue prematurely from the study. The same evaluations performed at final visit will be completed at the time of termination. If withdrawal is due to inability to tolerate investigational drug or other untoward event related to investigational drug, the withdrawal will be noted in data analysis as treatment failure.

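### A stopping-rule trigger automatically halts only enrolment; the week-8 and week-16 dose increases of patients already on resveratrol are not held during the safety review

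*Combined protocol and SAP*

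**What the plan says.** **What a trigger sets off.** Section 13.1.3 lists three triggers: a death thought to be drug-related, several medically similar related SAEs, and events that lead the principal investigator to judge that more subjects should not be dosed. The consequence of each is that "Study enrollment will be suspended pending expedited review of all pertinent data by the IRB and the DSMB". A prompt cumulative review then decides on re-opening entry, changing the protocol or ending the study. The section closes: "Review and approval by the DSMB is required for resumption of the study in the event the study is interrupted". Section 7.2, covering death and unexpected attributable Grade IV SAEs, says "enrollment will be suspended, pending Data Safety Monitoring Board (DSMB) review".

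**Wider powers.** Section 13.1.1 gives the DSMB, FDA and IRB authority to stop the trial, and introduces its list of grounds, which includes early stopping rules having been met, with "This study may be suspended or closed if". Section 7.1(f) lets the investigator end participation when it is not in the participant's "best medical interest to continue to participate in the study". The last bullet of 13.1.4 reads: "The investigator determines that the participant should be withdrawn from the study for reasons not listed above".

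**Escalation.** Section 5.6 starts patients at 250 mg daily, moves to 500 mg after 8 weeks and to 1000 mg at week 16. The condition is individual: "If no adverse effects are seen, patients should reach a dose of 1000mg per day at week 16 of the study". The reason given for this strategy is that "there is no previous data from human studies to demonstrate the safety of resveratrol in combination with sirolimus".

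**The concern.** The automatic restriction protects people who have not yet entered. In a trial with within-patient escalation, the people next due a higher dose are those already enrolled, and the enrolment hold does not reach them. The protocol does not say whether a step that falls due during the review goes ahead. It schedules that step, and makes it depend on that patient's tolerance alone.

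The gap matters because escalation is the protocol's own answer to having no human safety data on the combination. If a drug-related death occurs, whether to raise other patients' doses during the review should be settled in advance and not left to someone remembering to intervene. After the last patient enters, the review still takes place, but the only automatic restriction has lost its object while patients are still moving up to 1000 mg.

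**Working it through.** **1. The text, side by side.**

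| Provision | Automatic or discretionary | Pauses other patients' dose steps? |
|---|---|---|
| 13.1.3 and 7.2: enrolment hold | Automatic | No, entry only |
| 13.1.3: cumulative review | Automatic | Only if the review so decides |
| 13.1.1: suspend or close the study | Discretionary (*may*) | Only if invoked |
| 7.1(f), 13.1.4 last bullet | Discretionary | No; they remove a patient, not a step |
| 12.3.2: hold for a related AE of Grade 3 or higher | Automatic | No, affected patient only |
| 5.6: fall back to last tolerated dose | Follows that patient's intolerance | No |
| 6.3: week-8 and week-16 visit lists | Dispensing listed | No check for an open safety review |

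No row automatically holds a scheduled increase in a patient other than the one with the event. The resumption sentence in 13.1.3 speaks of the study being interrupted, but the only automatic interruption that section defines is of entry.

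**2. Inputs for the size.**
- 25 patients (6.4). Section 15 derives this from 20 evaluable and 20% dropout: 20/(1 − 0.2) = 25, which reproduces.
- Accrual over 15 months (6.1) = 15 × 52/12 = 65 weeks.
- 24 weeks on drug (Synopsis), with steps at weeks 8 and 16 (5.6), so 2 × 25 = 50 planned steps.
- Assumed: uniform accrual, no dropout, and a review of 2 to 4 weeks (no length is given).

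**3. While enrolment is open and accrual is in steady state.**
- Entry rate: 25/65 = 0.385 per week.
- On drug: 0.385 × 24 = 9.2 patients.
- With at least one step ahead: 0.385 × 16 = 6.2 patients.
- Steps: 2 × 0.385 = 0.77 per week, giving 1.5 in 2 weeks and 3.1 in 4 weeks.

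**4. After enrolment closes.**
- Week-8 steps: 25 × 8/65 = 3.1. Week-16 steps: 25 × 16/65 = 6.2. Together 9.2 of 50 (18.5%).
- Share of all treatment time: 24/(2 × 65) = 18.5%.
- Share of 1000-mg time: patients who entered in the last 16 weeks have all 8 weeks of it after closure, and those who entered 16 to 24 weeks before closure have 4 on average. (16 × 8 + 8 × 4)/(65 × 8) = 160/520 = 30.8%.

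**5. Sensitivity.**
- 20% dropout at a constant rate over 24 weeks, so the fraction remaining at week t is 0.8^(t/24): 0.928 at week 8 and 0.862 at week 16. Planned steps become 25 × (0.928 + 0.862) = 44.8. Steps per week are 0.385 × 1.790 = 0.69, giving 1.4 to 2.8 in 2 to 4 weeks. After closure: 0.385 × (8 × 0.928 + 16 × 0.862) = 8.2. On drug at a time: 8.3. With a step ahead: 5.7.
- Accrual over 12 months (52 weeks), no dropout: 25 × 24/52 = 11.5 of 50 steps after closure. Over 18 months (78 weeks): 25 × 24/78 = 7.7 of 50.

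**The case against.** The case for leaving the text alone is that the protocol has ample power to act:
- The DSMB, FDA and IRB can halt the trial at any time, and investigator belief that it is unsafe is a separate ground for suspension (13.1.1).
- Section 14.12.1.2 exempts participant-safety changes from the need for prior IRB approval, so a pause would not have to wait for an amendment.
- The affected patient has a mandatory hold under 12.3.2.
- This is a single site whose principal investigator is also the IND sponsor and hears of SAEs at once, so a step going ahead in ignorance is unlikely.
- Section 9.1.2 reports no resveratrol-related adverse effects at doses up to 1 g per day.
- The exposure figures are conditional on a trigger, whose probability nobody has estimated, and on an assumed review length.
- The closure point is close to a truism, and replacement of non-evaluable patients (13.3) can re-open entry.
- The proposed fix itself leaves current dosing to judgement.

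Much of this stands as context. The powers exist, the review continues after closure, replacement is a small exception, and treatment time after closure is not unsupervised. But every study-level power listed is one that somebody must choose to use, and the one mandatory hold covers only the affected patient. The tolerability data do not concern the combination, and a trigger means that expectation is in doubt. Treating a step differently from current dosing is also reasonable: a step raises exposure beyond what that patient has taken in this study, while interrupting treatment is a larger decision that merits case-by-case review.

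**Conclusion.** The concern holds. On a trigger, the enrolment hold is the only automatic restriction, and it does not reach the patients whose doses are scheduled to rise. Restraint on those steps is available but discretionary.

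The reading of the text needs no assumptions. The size does: under even accrual over 15 months without dropout, a review of 2 to 4 weeks would overlap about 1.5 to 3 scheduled increases, and about 9 of 50 increases (8 to 12 if accrual takes 18 to 12 months) come after the enrolment hold has ceased to matter. These describe what would be exposed if a trigger occurred; they are not a forecast that one will. This is a weakness in a safety rule, cheap to repair and worth repairing. It does not bear on the validity of the VEGF-D analysis.

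**What to change.** Amend 7.2 and 13.1.3 along these lines:
- When a trigger is met, whether or not enrolment is still open, enrolment and all scheduled resveratrol dose increases are automatically held until the DSMB review is complete.
- The DSMB and investigators promptly decide whether current dosing is also held.
- DSMB approval is required before enrolment and dose increases resume. This replaces the present reference to resuming the study.

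In 6.3, add to the week-8 and week-16 visits that a patient seen during a hold is dispensed her current dose, unless dosing is also held.

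The cost is a few sentences, plus some delayed steps if a trigger occurs. If the week-24 visit keeps its date, a week-16 step delayed by 2 to 4 weeks leaves 8 − 2 = 6 to 8 − 4 = 4 weeks at 1000 mg before the primary VEGF-D measurement, in place of 8.

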#### **13.1.4 Individual early stopping rules**

A study participant will be terminated from the study if any of the following occurs during the study:

- Recurrent or persistent resveratrol-related toxicity unresponsive to treatment in spite of dose adjustments.
- Pregnancy or failure to comply with adequate contraception
- The participant refuses to continue in the study
- Continued non-compliance
- The investigator determines that the participant should be withdrawn from the study for reasons not listed above

A subject will be considered evaluable if they receive treatment for at least 8 weeks and the relevant information collected during this period. Subjects who are withdrawn after less than 8 weeks of treatment will be considered as pre-mature discontinuation, and will be replaced by another participant.

Every effort will be made to obtain endpoint evaluations for subjects who withdraw or who discontinue prematurely from the study. The same evaluations performed at final visit will be completed at the time of termination. If withdrawal is due to inability to tolerate investigational drug or other untoward event related to investigational drug, the withdrawal will be noted in data analysis as treatment failure.

#### **13.2 Follow-up after early study termination**

Participants who are prematurely withdrawn from study drug exposure due to adverse events will be followed to monitor safety for a minimum of 30 days or until resolution or stabilization of the disqualifying event or until the Principal Investigator determines that further follow-up is not needed.

Subjects considered “lost-to-follow-up” are those enrolled in the study, but, for whatever reason, refuse to return to complete the study per the protocol. Reasonable efforts will be made to contact any subject lost to follow-up during the course of the study in order to complete assessments and retrieve any outstanding data, study drugs or clinical supplies. The investigator must make at least three documented attempts to have the patient return for study withdrawal evaluations.

#### **13.3 Participant replacement**

Participants with early termination from this study will be replaced if they are deemed non-evaluable.

## **14. Data and Safety Monitoring Plan**

The study protocol will be reviewed and approved by the DSMB and University of Cincinnati IRB prior to study initiation. Participant enrollment may only begin with IRB approved consent forms. This is an interventional exploratory phase II study.

### **14.1 Study Oversight**

The Principal Investigator has primary oversight responsibility of this clinical trial. The DSMB has oversight responsibility of the Data Safety Monitoring Plan (DSMP) for this clinical trial. The DSMB will review accrual, patterns and frequencies of all adverse events, and protocol compliance every 6 months. The DSMB makes recommendations to the PI regarding the continuation status of the protocol.

The site Principal Investigator and their research team (co-Investigators, research nurses, clinical trial coordinators, and data managers) are responsible for identifying adverse events. Aggregate report - detailed by severity, attribution (expected or unexpected), and relationship to the study drug/study procedures – will be available for site review.

### **14.2 Adverse Events**

This section defines the types of adverse events and outlines the procedures for appropriately collecting, grading, recording, and reporting them. Information in this section complies with ICH Guideline E2A: Clinical Safety Data Management: Definitions and Standards for Expedited Reporting and ICH E6: Guideline for Good Clinical Practice, and applies the standards set forth in the National Cancer Institute (NCI), Common Terminology Criteria for Adverse Events version V 4.0. These criteria have been reviewed by the study investigators and have been determined appropriate for this study population.

### **14.3 Definitions**

#### **14.3.1 Adverse events**

An adverse event (AE) is any occurrence or worsening of an undesirable or unintended sign, symptom, laboratory finding, or disease that is experienced during participation in the trial. An AE can therefore be any unfavorable and unintended sign (including an abnormal laboratory finding), symptom, or disease temporarily associated with the use of a medicinal (investigational) Study Agent(s) or a study procedure, whether or not related to the medicinal (investigational) Study Agent(s) or study procedure. Any medical condition that is present at the time that the subject is screened will be considered as baseline and not recorded as an AE. However, if the condition deteriorates or changes in severity at any time during the study it will be recorded and reported as an AE.

#### **14.3.2 Suspected adverse reaction and adverse reaction**

Suspected adverse reaction (SAR) means any adverse event for which there is a reasonable possibility that the drug caused the adverse event. For the purposes of safety reporting, ‘reasonable possibility’ means there is evidence to suggest a causal relationship between the drug and the adverse event. A suspected adverse reaction implies a lesser degree of certainty about causality than adverse reaction, which means any adverse event caused by a drug.

An adverse reaction (AR) means any adverse event caused by a drug. Adverse reactions are a subset of all suspected adverse reactions for which there are reasons to conclude that the drug caused the event.

#### **14.3.3 Adverse events associated with study procedures**

The following clinical situations will be considered to be outside of the normal range of findings and will be recorded as Adverse Events. These situations do not limit the principal investigator from reporting any other events, associated or not with these procedures, from being recorded and reported as AEs.

Blood draws

- Fainting/vasovagal events
- Bruising at puncture site greater than 2 cm in diameter
- Bleeding from puncture site lasting more than 5 minutes
- Swelling at puncture site larger than 2 cm

Pulmonary function testing

- Wheezing or bronchoconstriction requiring treatment with bronchodilators within 30 minutes from the procedure
- Coughing requiring treatment with bronchodilators within 30 minutes from the procedure

Adverse events related to study medication will be tabulated by body system and by severity using the NCI CTCAE v4.0.

#### **14.3.4 Serious Adverse Event (SAE)**

An AE or SAR is considered “serious” if it results in any of the following outcomes (21 CFR 312.32(a)):

- Death: A death that occurs during the study or that comes to the attention of the investigator during the protocol-defined follow-up.
- A life-threatening event: An adverse event or suspected adverse reaction is considered “life-threatening” if, in the opinion of the investigator, its occurrence places the subject at immediate risk of death. It does not include an adverse event or suspected adverse reaction that, had it occurred in a more severe form, might have caused death.
- An inpatient hospitalization or prolongation of existing hospitalization.
- Persistent or significant disability/incapacity or substantial disruption of the ability to conduct normal life functions.
- An important medical event that may not result in death, be life threatening, or require hospitalization may be considered an SAE when, in the opinion of the investigator, it may jeopardize the participant and may require medical or surgical intervention to prevent one of the outcomes listed above.
- Congenital anomaly or birth defect.

Regardless of the relationship of the adverse event to the study, the event will be reported per Section 14.3.4 as an SAE if it meets any of the above definitions.

### **14.3.5 Expected adverse events**

This section lists those adverse events regarded as expected for resveratrol:

Gastrointestinal: Nausea, vomiting, diarrhea, abdominal discomfort, flatulence

General: Fatigue

Hematological: Anemia, thrombocytopenia

Renal: Acute kidney injury

Liver: Increased serum bilirubin

Infectious: Increased risk of infections

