Exclusion Criteria	
Subjects who meet ANY of the following criteria are not eligible for enrollment as study participants:
 
 
1. Known allergy or hypersensitivity to Resveratrol
 
2. Inability to provide informed consent
 
3. Active enrollment in other clinical drug trials for LAM
 
4. Pregnant or plan to become pregnant in the next 6 months
 
5. Breast feeding
 
6. Inability to comply with pulmonary function tests or follow up visits
 
7. Inadequate contraception
 
8. Use of estrogen containing medications within the 30 days prior to randomization
 
9. History of organ transplant
 
10. Actively listed for lung transplantation
 
11. Inability to comply with study procedures or attend scheduled study visits
 
12. Any clinically significant medical disease (other than LAM) that is associated with an expected survival of less than 2 years, or likely to impact the ability of the patient to participate in the study in the opinion of the investigator, or impact the study efficacy or safety assessments.
 

Investigational Product	Resveratrol at escalating doses starting at 250mg per day to a maximum of 1000mg per day

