#### 9.1.2 Safety Profile of Resveratrol in Humans

In general, resveratrol is a well-tolerated drug with a robust safety profile. No adverse effects related to resveratrol were reported in clinical studies evaluating doses up to 1 gram of resveratrol per day (50-55). Resveratrol is well tolerated even at higher doses, however there is an increase in the gastrointestinal side effects at doses exceeding 1 gram per day. Howells et al. conducted a phase I study evaluating the safety profile of a micronized oral formulation of resveratrol in patients with liver metastases of colorectal cancer. Six patients received 5 grams per day of resveratrol for a total of 14 days. Resveratrol was well tolerated, in general, with the most common adverse effects being mild nausea and diarrhea. Other adverse effects included chills, lethargy, rash, peripheral neuropathy, skin irritation and vascular flushing, which resolved without sequelae (49). Using the same dose and formulation in 24 patients with multiple myeloma, Popat et al. noticed a higher rate of development of adverse effects. The most commonly reported adverse events were: nausea (79%), diarrhea (71%), vomiting (54%), fatigue (46%) and anemia (38%). 54% of patients reported grade 3 adverse events; most commonly 21% hematological (anemia and thrombocytopenia), 21% renal failure, 13% nausea and 13% infections (56).

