In a phase I study, 10 healthy volunteers were given 4 different strengths of resveratrol (0.5 grams, 1 gram, 2.5 grams and 5 grams per day). Resveratrol was well tolerated at all doses, with no serious adverse effect noted. Minor adverse events were seen in 57% of the patients, and were self-limited resolving 2-4 days post administration (45). The same study was repeated again yielding similar results. There were no serious adverse events related to resveratrol. However, subjects taking the higher dose of resveratrol (2.5 grams and 5 grams per day) had an increased incidence of gastrointestinal symptoms, including nausea, flatulence, abdominal discomfort and diarrhea. Most of these events were mild (severity grade 1, NCI CTCAE v.4.0), although 4 participants on the 2.5 gram and 5 gram doses presented with nausea and/or diarrhea of moderate severity (grade 2). The gastrointestinal side effects commenced after 2-4 days of the intervention and occurred half to one hour after resveratrol ingestion (42). Other studies have reported similar findings with an increase in the incidence of gastrointestinal side effects at resveratrol doses higher than 1 gram per day, with most side effects being mild and spontaneously resolving after a brief drug holiday (41, 44, 47, 57, 58). Due to the increased incidence of gastrointestinal side effects related to resveratrol at high doses (42), and the increased incidence of renal failure noted in one study (56), we have decided to limit the highest dose in our study at 1 gram per day.

Adverse reaction	Incidence (%)
Gastrointestinal disorders	
Nausea	10 - 15
Vomiting	8 - 12
Diarrhea	20 – 30
Flatulence	5 – 10
Abdominal discomfort	5 - 10
Nervous system disorders	
Headache	< 1
Peripheral neuropathy	< 1
General disorders	
Fatigue	< 5
Chills	< 1
Musculoskeletal disorders	
Myalgias and muscle cramps	< 1
Skin and subcutaneous tissue disorders	
Rash	< 1
Skin discoloration/irritation	< 1
Acne	< 1
Flushing	< 1
Hematologic disorders	
Anemia	2 - 4
Thrombocytopenia	2 - 4
Renal disorders	
Acute renal failure	0 – 4%
Laboratory abnormalities	
Elevated bilirubin	< 1

**Table 1:** Adverse reactions associated with the use of resveratrol (41, 42, 44, 45, 47, 49, 56-58). Percentages for the incidence of a particular adverse event are estimated after combining the patient numbers in clinical studies evaluating high dose resveratrol.

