### **14.8.2 Notifying the FDA**

The IND sponsor (The PI) is responsible for FDA safety submissions as follows: The IND Sponsor for this study will handle all regulatory communications with the Food and Drug Administration and will be responsible to update the IND to include this trial, file all regulatory related issues including any MEDWATCH reports which will be reviewed and approved by the PI and Steering Committee. The IND sponsor will be responsible for submission of yearly reports and final report for this study. All DSMB recommendations will be communicated to the IND sponsor in a timely fashion.

The following process for reporting a serious adverse event ensures compliance with the ICH guidelines, 21CFR §312.32.

- Expedited safety report to the FDA applies if the adverse event is classified as one of the following:
  - Serious and unexpected suspected adverse reaction (SUSAR) (Sections 14.3.4, 14.3.6, and 14.7) (i.e. serious, unexpected, and related)

Or
  - Aggregate analysis of adverse events that suggest a causal relationship to the study medications

Or
  - Any findings from clinical, epidemiological, pooled analysis of data pooled across multiple studies, published or unpublished scientific papers or any findings from animal or in vitro testing that would result in a safety-related change in the protocol, informed consent, investigator

brochure or other aspects of the overall conduct of the trial will be reported.

Expedited Safety Reports must be reported by the IND Sponsor to the FDA within 15 calendar days; fatal or immediately life-threatening serious, unexpected, suspected adverse reactions must be reported within 7 calendar days. SAEs that do not strictly fit the above criteria may be reported to the FDA in an expedited manner if the IND Sponsor chose to do so. Each 7-day report must be followed up by a 15-day report.

The following types of SAEs will be reported in the IND Annual Report:

- Serious, expected, suspected adverse reactions
- Serious but not a suspected adverse reaction

For standard reporting, the IND Sponsor or designee will file the IND Annual Report. All adverse events (not just those requiring 24 hour reporting) will be reported in the Annual IND Report.

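### Section 14.3.5 lists kidney injury, anemia, thrombocytopenia and infections as expected without dose or grade, so a first isolated serious case can miss the expedited FDA report

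*Combined protocol and SAP*

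**What the plan says.** Section 14.3.5 is introduced by "This section lists those adverse events regarded as expected for resveratrol". It names gastrointestinal events, fatigue, anemia, thrombocytopenia, acute kidney injury and raised bilirubin, and ends with "Infectious: Increased risk of infections". No entry carries a grade, a dose or a frequency.

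The trial's own doses are given in the Synopsis: "Resveratrol at escalating doses starting at 250mg per day to a maximum of 1000mg per day". For that range, section 9.1.2 states: "No adverse effects related to resveratrol were reported in clinical studies evaluating doses up to 1 gram of resveratrol per day". The same section describes grade 3 renal failure (21%), grade 3 hematological events, namely anemia and thrombocytopenia (21%), and grade 3 infections (13%) in 24 myeloma patients at 5 g/day. It then gives two reasons for its ceiling, gastrointestinal effects at high dose and the renal failure in that one study: "we have decided to limit the highest dose in our study at 1 gram per day".

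Table 1 in section 9.1.2 gives acute renal failure as 0–4% and anemia and thrombocytopenia as 2–4% each. Its caption says that the percentages "are estimated after combining the patient numbers in clinical studies evaluating high dose resveratrol".

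Section 14.3.6 calls an event unexpected when its nature, severity or frequency does not fit the information in the protocol. Two rules for serious events then use the label. Under 14.8.2, a single-case expedited FDA report needs an event that is serious, related and unexpected; serious expected reactions go to the IND Annual Report. Under 7.2, enrollment is suspended for a death or for a "Grade IV Serious adverse event (SAE) attributable to the study agent and unexpected".

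**The concern.** The protocol lowers its dose ceiling partly because of a renal signal, reports no resveratrol-related effects at or below that ceiling, and then lists the renal event as expected with no dose attached. Anemia, thrombocytopenia and infections are in a similar position: the text describes them only at 5 g/day.

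Section 5.6 says there are no earlier human data showing the safety of resveratrol with sirolimus in LAM, and section 12.3.5 anticipates that resveratrol may raise sirolimus levels. In that setting the first serious case of one of these events is the informative one. If it can be labeled expected, it can reach the FDA only with the annual report. The label is also decided close to home: the Principal Investigator determines causality (14.8) and is the IND sponsor (14.8.2).

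**Working it through.** The plan states no figure of its own to reproduce. The check sets the passages side by side and then sizes the gap.

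**1. Dose ratio.** Myeloma study dose ÷ trial maximum = 5 g ÷ 1 g = 5. Against the 500 mg and 250 mg steps it is 10 and 20.

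**2. Patients behind the signal.** 21% × 24 = 5.04, so about 5 patients with renal failure and about 5 with hematological events. 13% × 24 = 3.12, so about 3 with infections. The title of reference 56 shows that bortezomib was given as well.

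**3. One serious, related, grade 3 kidney injury at 1 g/day or less, tested under 14.3.6.**

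| Source in the protocol | What it implies |
|---|---|
| 14.3.5 list | Expected: named, no dose or grade limit |
| 9.1.2 narrative, doses up to 1 g/day | Unexpected: no related effects reported |
| 9.1.2 narrative, 5 g/day | Severity fits: grade 3 is described |
| Table 1, renal failure 0–4% | Frequency fits: 1 ÷ 25 = 4.0%, the top of the range |

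No text says which source prevails, or how one case is to be compared with a pooled range. Either classification can be defended.

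**4. The same event at Grade IV.** The narrative describes nothing above grade 3 for these four events, so a Grade IV case can be argued unexpected on severity. The list sets no grade limit, so the opposite can also be argued. A grade 3 event is outside the Grade IV trigger in 7.2 however it is labeled.

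**5. Rules that do not depend on expectedness.**
- 13.1.3: related death, multiple medically similar related SAEs, or Principal Investigator judgment suspends enrollment.
- 14.4.3: reportable SAEs are due within 24 hours or 5 working days.
- 14.8.3: safety reports go to the DSMB on an ongoing basis.
- 14.8.2: aggregate findings are expedited to the FDA.

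A second similar serious related case is caught by 13.1.3. A single non-fatal case is not, unless the Principal Investigator acts. The gap is therefore the isolated first case.

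**6. How likely is exactly one case?** Take n = 25 and a true renal failure risk p. The documents give no risk for this trial's doses, so p is assumed: 1%, 2%, or 4% (the top of Table 1).

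P(at least 1) = 1 − (1 − p)^25. P(exactly 1) = 25 × p × (1 − p)^24. P(at least 2) is the difference.

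| p | P(at least 1) | P(at least 2) | P(exactly 1) |
|---|---|---|---|
| 1% | 0.22 | 0.03 | 0.20 |
| 2% | 0.40 | 0.09 | 0.31 |
| 4% | 0.64 | 0.26 | 0.38 |

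These are chances of a case of any seriousness. The chance of a case that is also serious, related and classed as expected is smaller, and the documents do not allow it to be calculated.

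**The case against.** The strongest reply is that listing does not decide expectedness. Section 14.3.6 tests nature, severity or frequency against the whole protocol, and that includes the statement about doses up to 1 g/day. A careful sponsor could call the case unexpected today. Section 14.8.2 also lets the sponsor expedite other SAEs by choice, and the rules in step 5 of the working apply in any event. This stands, and it limits the point to one isolated case decided by judgment.

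Three stronger readings are tempting, and the documents do not support them.

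- A reader might infer that the whole expected list comes from studies at five times the maximum dose. It does not. Table 1 cites nine references, the text describes one study with 0.5, 1, 2.5 and 5 g/day, and gastrointestinal effects are described at 2.5 as well as 5 g/day. Whether lower-dose studies added renal or hematological cases to Table 1 cannot be told from the protocol.
- A reader might infer that the safety rules are switched off for these events. They are not, for the reasons in steps 4 and 5.
- A reader might infer that every rule using the word unexpected is affected alike. Section 14.8.1 covers only non-serious events, and 14.10.4 has its own test, which includes the characteristics of the population.

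It can also be said that capping a dose to lower a risk does not make the risk unforeseen, and that infections are plausible in patients taking an immunosuppressant. Table 2 in section 12.3.1 lists infections as an overlapping toxicity, with sirolimus to be reduced first, and 12.3.3 attributes known sirolimus toxicities to sirolimus alone. Some infections may therefore fail the relatedness test before expectedness matters. That weakens the point for infections. It does not remove the conflict between 14.3.5 and 9.1.2 for kidney injury, anemia and thrombocytopenia.

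**Conclusion.** The point holds for four entries and one situation. An isolated, serious, non-fatal case of kidney injury, anemia, thrombocytopenia or infection that is judged related to resveratrol can be classed as expected. It can then go to the IND Annual Report instead of an expedited FDA report. If Grade IV, it can also miss the 7.2 suspension, but less clearly, because severity gives an argument the other way.

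For renal failure, an isolated case of any seriousness is a realistic outcome: about 20% to 38% over assumed risks of 1% to 4%. The size rests on those assumed risks, on 25 treated patients and on independence between patients.

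This should be fixed. It is an unresolved inconsistency in how a safety signal is labeled. It is not a failure of safety oversight, and it does not touch the efficacy analysis.

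**What to change.** Reconcile 14.3.5 with 9.1.2, for safety classification only:

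1. Remove acute kidney injury, anemia, thrombocytopenia and infections from the expected list, or state that they are not treated as expected at this trial's doses for 14.8.2, 14.8.1 and 7.2.
2. Keep the gastrointestinal and fatigue entries, which section 5.5 also names as common side effects. Cutting the list to events documented at up to 1 g/day could, read against 9.1.2, empty it and create needless reports of gastrointestinal events.
3. Label Table 1 as high-dose reference, not as the frequency benchmark for this trial.
4. State in 14.3.6 that the revised 14.3.5 is the reference for expectedness.

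No dose, treatment rule or analysis changes. The cost is wording, plus possibly a few more expedited reports. As a guide, if Table 1's upper rate of 4% applied to kidney injury, anemia and thrombocytopenia, the expected number would be 25 × 0.04 = 1 of each, or 3 events of any grade, of which only the serious and related ones would be expedited to the FDA. Related non-serious events of Grade 3 or higher would move to the 24-hour procedure in 14.8.1. Table 1 has no rate for infections, so their contribution cannot be estimated in the same way.
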